Conditioned pharmacotherapeutic effects in Psoriasis. Of direct and immediate relevance to the proposed research are the results of a recently completed study (30) conducted at Stanford University and the University of Rochester. In this study, a conditioning component was added to a regimen of topical corticosteroid therapy for

for the reduced cumulative amount of active drug received by the Partial Reinforcement Group, received medication packets each of which contained 25-50% of the dose of steroid previously received. A physician, unaware of group assignments, conducted clinical evaluations weekly using a modified 9-point Psoriasis Severity Scale (PSS). As in the proposed research, it was hypothesized that “relapse,” defined here as a return to within two units of the initial PSS score, and disease severity would be less in patients treated under a intermittent schedule of pharmacologic reinforcement than in patients treated with the same cumulative amount of drug under a continuous schedule of reinforcement. As shown in Fig. 3, the results conformed precisely to predictions: the incidence of relapse in the Partial Reinforcement Group was significantly less than in Dose Control patients. There were no significant differences between the Partial Reinforcement and the Standard Therapy Groups.

There are a number of questions that need to be addressed to get beyond the inference that these results were due to conditioning. It could be argued, for example, that the reduced amount of drug received by the Partial Reinforcement Group was actually an effective dose of medication for psoriasis. However remote that possibility, we have, in the proposed research, added a second Dose Control Group that is treated with drug under the same conditions as the Partial Reinforcement Group but receives no intervening exposures to the CS. Nonetheless, the conclusion to be drawn from this first ever study of conditioned pharmacotherapeutic effects and the hints provided by the studies described above is that it is possible and feasible to introduce an intermittent schedule of pharmacotherapeutic reinforcement into a drug treatment regimen. And, it may indeed be possible to reduce the amount of drug required to control the symptoms of a disease by capitalizing on conditioned pharmacotherapeutic responses.

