The choice of the β/α blocker for this study was based on:

a) targets receptors of the peripheral nervous system (PNS); it is a non-selective β -adrenergic blocking agent with alpha-1 blocking activity. It is approved for use in hypertension as well as heart failure. Other hypotensive drugs could have been chosen, however, their primary target is not “directly” aimed at the PNS or CNS. We are aware that ACE inhibitors decrease catecholamines, and angiotensin receptor blockers decrease vasopressin, however, for this initial study we chose a drug that is mostly associated to the sympathetic system. We believe that this will provide the best chances of success. Future studies will include alternative drugs.

b) Carvedilol has no adverse effect on glycemic control, and is the preferred β blocking agent for patients that have diabetes (as some of ours may).

c) We have preliminary published data (28) that strongly suggests the effectiveness of our conditioning paradigm in the pharmacotherapy of hypertension using a similar β blocker.

d) can be administered two times a day, leading to an enhanced number of “learned” exposures to the stimulus, and this regimen guarantees that subjects in groups that receive only one active drug

administration out of 4 will take adequate daily amounts of that will prevent them from the undesired rebound side effects of this medication that could occur if they were to have 3 days with no active drug.

Subjects will be started on the lowest recommended starting dose of 25 mg daily in 2 fractionated doses, which is reasonable given their level of hypertension (33,34). Once a reasonable blood pressure drop is achieved, they will be randomized to four experimental groups, as described in the methods section.

Potential participants will be informed that the purpose of the study is to determine if their blood pressure could be brought under control using lower amounts of medication and that, in the course of the study, the amount of medication they receive may be reduced. The medical staff with whom the patient comes in contact will not know if or when this occurs. Measurement of blood pressure during the study will be performed by the patients themselves, who will be instructed in the use of automated BP monitors (HEM-711AC, Omron Healthcare Inc., Bannockburn, IL) which will be provided. Subjects will obtain measurements twice (one after the other) in the AM and twice (one after the other) in the PM always at the same time of day.

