A screening physical examination will be performed within one week of admission into the study and only patients, who are in good health, display no contraindications for the use of beta blockers and disclaim the use of antihypertensive medication for at least 2 wk. before the start of the study will proceed to the initial maintenance or baseline period.

Patients will be excluded from participation if they use illicit drugs, were using anti-hypertensive medications within the previous 2 weeks other than ACE-inhibitors, angiotensin receptor blockers, calcium channel blockers, aldosterone antagonists, or diuretics **Patients will be excluded from participation if they use illicit drugs; they use inhalers regularly to control reactive airway diseases like COPD and asthma;** if pregnant or if sexually active women are not using contraceptives; if they cannot be followed or monitored appropriately; or renal insufficiency are determined, which may require a blood draw at the time of screening physical examination if subject has not had basic blood profile done in the past 12 months.

Experiment 1. Effects of a partial schedule of pharmacotherapeutic reinforcement in maintaining the therapeutic effects of in the treatment of hypertension.

The proposed research will determine if, capitalizing on conditioned pharmacotherapeutic effects, patients suffering from hypertension can be effectively treated with smaller cumulative amounts of a beta blocker, . Some patients in this initial experiment will be treated on a partial rather than a continuous schedule of pharmacologic reinforcement. These patients will be compared to: (a) patients that continue to be treated on a standard regimen of pharmacotherapy at the baseline dose, and (b) patients that receive the same (reduced) total amount of medication under a continuous schedule of reinforcement as that received by experimental patients being treated under a partial schedule of reinforcement, and another Dose Control Group that receives at the same dose and frequency as the Partial Reinforcement Group, but receives no interspersed exposures to the CS.

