Patients in a **Standard Therapy Group** will continue to receive 100% of the dose of medication on the same reinforcement schedule (100%) as they received during the baseline (maintenance) period. (12.5 mg) would be taken 2 times daily for 15 additional days. This is a continuation of their standard pharmacotherapeutic maintenance regimen and constitutes one control group.

The **Partial Reinforcement Group** will be treated under a partial (25%) reinforcement schedule. That is, patients will receive the same dose of drug previously received, but only a quarter of the daily packets will contain active drug (12.5 mg); the remaining capsules will contain only an inert substance. Packets will be arranged to ensure that a patient never receives the “placebo” for more than two consecutive times. The selection of a 25% reinforcement schedule is based on the fact that we are using the minimum recommended starting dose of , and lower doses (particularly this much lower) are likely to have minimal if any pharmacologic effect. Therefore, the total daily dose of 6.25 mg. would not be sufficient to sustain the normotensive levels achieved under continuous reinforcement during the baseline period.

Dose Control Group-1, a control for the cumulative amount of drug received by the Partial Reinforcement Group, will be treated twice daily under a continuous (100%) reinforcement schedule, but each packet will contain only 25% of the active drug received during the baseline period.

To be sure that the reduced amount of drug received by the Partial Reinforcement Group is not sufficient by itself to lower blood pressure, a **Dose Control-2 Group** will receive the same active dose as the Partial Reinforcement Group but will not receive CSs on the intervening doses (6.25 mg once every other day).

Table 1. Experimental Protocol

GROUP	BASELINE PERIOD (15 days)			EXPERIMENTAL PERIOD (15 days)		
	Drug Dose*	Reinforcement Schedule**	Freq.	Daily Drug Dose***	Reinforcement Schedule**	Freq.
Standard Therapy	25	100	2xDay	25	100	2xDay
Partial Reinforcement	25	100	2xDay	6.25	25	2xDay

RSRB: 36447 12 V08.03.2016

Dose Control-1	25	100	2xDay	6.25	100	2xDay
Dose Control-2	25	100	2xDay	6.25	100	every other day

* Daily Dosage in mg of antihypertensive medication

** Percentage of treatment occasions when active drug is received

*** Average Daily Dosage in mg of antihypertensive medication

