The primary outcome measure will be the incidence and rate of “relapse,” defined as a blood pressure level that has risen to the baseline value (blood pressure value of the participant at the time of enrollment) for three consecutive days.

If, over the course of 15 days there is evidence of a gradual recurrence of symptoms, the experimental period can be extended. If there is no evidence of impending relapses, there are two options: (a) we can reduce the partial reinforcement schedule from 25% to 15%, for example, and adjust the dose of in the Dose Control Groups accordingly; or (b) proceed to a study of extinction effects (Experiment 2).

Timeline estimate. We propose a start-up period of 6 mo. (formulation of Consent Form, IRB approval of protocol, preparation of study personnel, data management procedures, preparation and placing of advertisements for study subjects, etc). Including an instructional session and testing of blood pressure measurements from the monitors provided to patients, patients enrolled in the study could be engaged for as many as 50-60 days. We calculate being able to process 40 patients/year. A final 6 mo. would be devoted to data processing and manuscript preparation and, thus, a total project period of 4 years.

Experiment 2. *Effects of CS exposure on the persistence of drug effects following the withdrawal of drug and the effects of partial schedules of pharmacotherapeutic reinforcement on resistance to extinction.*

Based on the time available and the outcome of Experiment 1, we may be able to gather additional preliminary data on the extinction of conditioned pharmacotherapeutic effects, adding evidence that results obtained in Experiment 1 are, in fact, the results of conditioning. We expect that patients in Dose Control Group-II from Experiment 1 will relapse within 2-3 days of the treatment imposed during the experimental period. A large percentage of Dose Control Group-I patients are also expected to relapse under a reduced dose of active drug during the experimental period. However, we expect that a significant percentage of patients in the Partial Reinforcement Group (as well as the Standard Therapy Group) would be available for further study of extinction effects.

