If, as anticipated, there are a sufficient number of patients from Experiment 1 who show no evidence of relapse within the 15-day experimental period, we can proceed to Experiment 2. The remaining patients from the Standard Therapy and Partial Reinforcement Groups (and, perhaps, the Dose Control Group-1) would be divided into two subgroups. For one subgroup, all medication would be discontinued for a period of 2-4 wk; for the other subgroup, active drug would be discontinued but the patients would continue to receive the distinctive capsules containing inert substance. It is predicted that: (a) patients reexposed to the CS will be less likely to relapse or show a slower rate of relapse than patients in groups that are not reexposed to the CS; and (b) patients in the Partial Reinforcement Group will be more resistant to extinction (slower to relapse) than patients remaining from Dose Control Group-1 who were treated with the same cumulative amount of drug and may even be indistinguishable from the Standard Therapy Group that had received three times more drug. An alternative strategy, of course, would be to enlist a new population.

c) Statistical Analysis: Data analyses are described separately for each of the specific hypotheses. All statistical tests will be two-sided with $p \leq .05$. The principal analyses focus on the difference over 2-weeks between PR and two dose control groups (DC-1 and DC-2) in Experiment 1. The main independent variable is time to relapse as well as symptom reduction (blood pressure). These two outcomes will also be examined in Experiment 2 to see if they differ between the two groups (placebo and no-treatment groups). Because power for the comparisons in the second experiment may be undercut by high relapse rates in the first experiment, this second set of analyses is exploratory.

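### The text gives Dose Control-2 half the daily dose shown in Table 1, and so half the nominal Partial Reinforcement dose it is meant to match

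*Combined protocol and SAP*

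**What the plan says.** Under Experiment 1 (section III), the paragraph on the Dose Control-2 Group reads in part: "the same active dose as the Partial Reinforcement Group but will not receive CSs on the intervening doses (6.25 mg once every other day"). In Table 1 the same arm has 6.25 in the experimental-period dose column, with frequency every other day. The footnote to that column reads "Average Daily Dosage in mg of antihypertensive medication".

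The arm it should match, Partial Reinforcement, keeps the baseline capsule strength on a 25% schedule: "only a quarter of the daily packets will contain active drug (12.5 mg"). Item d of the reasons for choosing the drug likewise describes groups with one active "administration out of 4 will take adequate daily amounts".

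The match is also stated in two other places. The introduction to Experiment 1 describes an arm that "receives at the same dose and frequency as the Partial Reinforcement Group, but receives no interspersed exposures to the CS". The psoriasis paragraph of the Preliminary Studies says the investigators added "a second Dose Control Group that is treated with drug under the same conditions as the Partial Reinforcement Group", to answer the objection that the reduced amount of drug might itself be effective.

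**The concern.** DC-2 exists to separate the drug from the conditioned stimulus: it should give PR's drug without the placebo capsules in between. DC-1 cannot do this alone, because it changes both the amount per capsule and the schedule. If DC-2 also receives less drug than PR, a difference between the two arms mixes the absent stimulus with a lower dose.

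The protocol predicts a quick failure in this arm: "We expect that patients in Dose Control Group-II from Experiment 1 will relapse within 2-3 days of the treatment imposed". At half the dose, that result would say nothing firm about the amount PR receives, and any dose effect would make PR look better. The comparison is not incidental. Section III c) states: "The principal analyses focus on the difference over 2-weeks between PR and two dose control groups (DC-1 and DC-2) in Experiment 1".

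**Working it through.** **Inputs, all from section III.**
- Baseline and Standard Therapy: 12.5 mg twice daily.
- PR: 12.5 mg on 25% of two daily occasions.
- DC-1: 25% of 12.5 mg, that is 3.125 mg, twice daily.
- DC-2 (text): 6.25 mg once every other day.
- Experimental period: 15 days, so 30 twice-daily occasions.

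**Average daily dose** = mg per active dose × active doses per day.

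| Arm | From the text | Table 1 |
|---|---|---|
| Standard Therapy | 12.5 × 2 = 25 | 25 |
| PR | 12.5 × 2 × 0.25 = 6.25 | 6.25 |
| DC-1 | 3.125 × 2 = 6.25 | 6.25 |
| DC-2 | 6.25 × 0.5 = **3.125** | 6.25 |

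Three rows reproduce exactly. DC-2 does not: 3.125 / 6.25 = 0.50.

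**Totals over 15 days.**
- PR, nominal: 0.25 × 30 = 7.5 capsules, or 93.75 mg on average. With 7 or 8 whole capsules the total is 87.5–100 mg.
- DC-1: 30 × 3.125 = 93.75 mg.
- DC-2 as in the text: 7 or 8 doses × 6.25 = 43.75–50 mg.
- DC-2 at 12.5 mg every other day: 7 or 8 × 12.5 = 87.5–100 mg.

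Dose for dose, the text regimen is 43.75 / 87.5 = 50 / 100 = 50% of nominal PR.

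**Can another reading of the sentence save it?** If its matching clause means the amount per capsule, PR's active capsule is 12.5 mg, not 6.25. If it means the average daily amount, PR's is 6.25 mg, not 3.125. The figure in parentheses fails both ways.

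**Which figure is consistent?** A quarter of two daily occasions is one active capsule per two days. At 12.5 mg once every other day, DC-2 averages 12.5 × 0.5 = 6.25 mg/day. That agrees with Table 1, PR's capsule strength and the matching statements. The likely source of the slip is that the daily average was written as the amount per dose.

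**The case against.** The mismatch itself is not in dispute. The case for treating it as minor is this.

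- **The intent is clear.** The matching clause sits in the same sentence, and the Medication paragraph describes only a 12.5 mg active capsule. The pharmacy may well have packed 12.5 mg. This is suggestive rather than decisive, because DC-1's 3.125 mg capsule is not described there either.
- **The arm is small.** DC-2 has 10 subjects against 37 in PR (section II b). The 93% power claim concerns groups 2 and 3, that is PR and DC-1. The pairwise relapse contrasts follow only if the overall group test is significant. This stands as a limit on reach.
- **The dose may not matter.** The protocol itself expects little or no pharmacologic effect at doses this low. But that is the assumption DC-2 was added to test, so it cannot excuse the mismatch.
- **The absolute gap may be small.** If DC-2 patients relapse within 2–3 days, they will have taken one or two doses: 6.25–12.5 mg instead of 12.5–25 mg. The ratio is still one half.
- **Table 1 alone would also allow 6.25 mg twice on alternate days.** Arithmetically this is so. The reading is strained, because the frequency column writes 2xDay when it means twice, and it would not match PR's 12.5 mg capsule.
- **PR's nominal 25% cannot be met.** This is correct. PR patients may not have more than two placebos in a row. With k active capsules in 30, this requires 30 − k ≤ 2(k + 1), so k ≥ 10. PR then gets at least 125 mg (8.33 mg/day). Against that minimum, the text regimen for DC-2 is 35–40% and the corrected regimen 70–80%. This is a separate defect. It makes the shortfall at 6.25 mg larger, and it means that correcting the DC-2 figure restores only the nominal match.

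**Conclusion.** The concern holds. The dosing instruction for a randomized arm contradicts the protocol's own table and its matching statements by a factor of two. The arithmetic is certain: 3.125 against 6.25 mg/day, both relative to the nominal 25% PR schedule.

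The consequence is conditional. It depends on the text regimen being the one dispensed, which the documents do not show, and on the missing 3.125 mg/day having some effect on blood pressure. With no dose-response data in the documents, the effect on relapse cannot be computed and may be near zero. If there is an effect, it favours PR. Hypothesis 1, tested by PR versus DC-1, is not affected by this error. The correction is nevertheless necessary, because the text as written defeats the purpose of the arm and PR versus DC-2 is among the principal comparisons.

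**What to change.** In the Dose Control-2 paragraph of Experiment 1, replace the dose in parentheses with 12.5 mg once every other day; Table 1 needs no change. Check the research pharmacy's packing instructions against this figure.

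If any DC-2 patient was treated with 6.25 mg every other day, report the actual cumulative milligrams by arm and do not describe DC-2 as dose-matched to PR. The conflict between the 25% schedule and the two-consecutive-placebo rule needs its own correction; whatever PR dose results should then be carried over to DC-2.

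The cost is one number in the text and one check with the pharmacy.

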- Subject population Characteristics: This investigation will apply the principles of conditioning described above in patients with mild (Stage 1) *hypertension*. These are patients who are normally started on a single drug and, most often, on the lowest dose recommended. In this case, we will be using, a drug currently used for the treatment of hypertension. Subjects will be 18-80 year old male and female patients **with mild hypertension** (systolic pressure between 140-170 and a **heart rate of 68 beats/minute or greater** . . .
- Number of available subjects: In the year 2004, the incidence of hypertension in the U.S. was 29% of the adult population, and rapidly rising. Patients will be recruited from the Medicine clinics of University of Rochester and affiliated Primary Care facilities. The pool of potential subjects is over 2,000.
- Acceptable disease status/condition (concomitant illnesses): Subjects should be in generally good health, and on few medications
- Must not suffer from severe or inhaler-dependent reactive airway disease (asthma or COPD).
- **Permitted or prohibited concurrent treatment:** the only classes of anti-hypertensive medications that can be used are ACE-inhibitors, angiotensin receptor blockers, calcium channel blockers, aldosterone antagonists, and diuretics. No other classes of anti-hypertensive medications are permitted.
- Time constraints for performance of pre-study (**eligibility**) tests: **If potential participant has not had blood work done within the** past year, a basic blood profile (one tube of blood) will be required to **ensure renal functions are safe for the use of carvedilol**. The blood draw can be done by research staff at the time of initial evaluation and available within 24 hours for review. Ability of the subject to provide informed consent: Only subjects able to provide informed consent will be recruited

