It is possible that the therapeutic effects of a partial schedule of pharmacologic reinforcement (and, thus, a reduced amount of active drug) will be indistinguishable from a continuous (standard) regimen of pharmacotherapy. That outcome, however, is not critical for evaluating the role of conditioning in pharmacotherapies simply because these groups would have received different amounts of drug. Specifically, *it is hypothesized that patients treated under a noncontinuous schedule of medication will be less likely to show a recurrence of symptoms ("relapse") than patients treated with that same amount of drug administered under a continuous schedule of reinforcement.*

On the first visit, each potential subject will undergo a brief physical examination to record the medical history, sign an informed consent form, and receive instruction in the use of a blood pressure monitor. A strip of medication packets will be supplied at each clinic visit and will be taken by the subject at home, 2

times a day for the duration of the study.. The subject will return to the study center once a week or within 14 days of the drug dispensing cycle; this will allow flexibility for those with travel or work schedule challenges. The study coordinator will email or call to check on safety of the subject in the interim of a weekly clinic visit. Each drug card contains 15 days of study drug to ensure continual dosing in the event a weekly visit is missed. Packets containing medication will be dispensed by code so the patient and the physician will be blinded as to the nature of the medication. To consider the possibility that conditioning might be influenced by immediate stressful life experiences in these patients, we will examine this relationship using two measures of psychological distress administered at weekly intervals: the Hassles Scale, a frequently-used measure of daily stressors or “hassles” and the Impact of Events Scale (IES) (31).

The protocol for Experiment 1 is shown in Table 1. During a baseline period (of a maximum of 15 days), all patients will be treated BID with 12.5 mg. Those who satisfy the criterion of a 10-point decrease in blood pressure for a period of 5 days will be assigned randomly to experimental groups.

During the 15-day experimental period, the patients will be treated as follows:

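### Relapse is scored against the enrolment blood pressure, a noisy and selected reference, so true relapses are missed and patients with no drug effect can be randomised

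*Combined protocol and SAP*

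**What the plan says.** Section III, Experiment 1 makes the incidence and rate of relapse the primary outcome. Relapse is "defined as a blood pressure level that has risen to the baseline value", explained as the "blood pressure value of the participant at the time of enrollment", and it must last "for three consecutive days". Section II.a admits patients with "systolic pressure between 140-170".

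Randomisation requires "a 10-point decrease in blood pressure for a period of 5 days". Neither the Experiment 1 text nor the length-of-study paragraph says what the fall is measured from, or whether it applies to the average of the five days or to each of them.

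The period called baseline is on study drug: "During a baseline period (of a maximum of 15 days), all patients will be treated BID". Outcome readings come from home: "Measurement of blood pressure during the study will be performed by the patients themselves", with two readings each morning and two each evening. The Schedule of Events places these readings in the study period only. It also lists vital signs at baseline; if taken before the first capsule, these are a visit measurement of the same kind as the enrolment value. No multi-day average before study drug is described, and neither is any adjustment for regression to the mean. The number of readings behind the enrolment value, the device and the pressure component are not stated.

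**The concern.** Three things push the reference above a patient's usual pressure, or make it uncertain.

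- **Noise.** A value from one occasion carries the whole visit-to-visit error.
- **Regression to the mean.** Where the source population lies below the middle of the entry window, patients admitted on a reading of 140-170 have on average a usual pressure below that reading.
- **Selection by the run-in rule.** If the fall is measured from the same value, the patients who pass are disproportionately those whose enrolment reading was high by chance.

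A reference that is too high makes the 10-point fall easier to reach without any drug effect. It also makes the relapse threshold harder to reach once the drug effect has gone. Patients who never responded cannot show a loss of response. Responders who do lose it may not be counted. Both reduce what the comparison of partial reinforcement (PR) with Dose Control-1 (DC-1) can show. Few scored relapses could also be read as no sign of coming relapse, which the plan treats as grounds for changing the schedule or moving to Experiment 2.

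**Working it through.** **The plan's own figure.** Section II.b states 93% power with 37 per arm, 10% dropout and two-sided alpha 0.05 for a 50% difference in relapse. It gives no control relapse rate, so the figure has no unique check. Reading it as 80% against 40% with 33 per arm (37 × 0.9 = 33.3):

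- SE under the null = √(2 × 0.6 × 0.4 / 33) = 0.1206
- SE under the alternative = √((0.16 + 0.24) / 33) = 0.1101
- z = (0.40 − 1.96 × 0.1206) / 0.1101 = 1.486, so power is 93.1%

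That reading reproduces the figure and is used below.

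**Assumptions.** The documents give no variance components. Assumed: between-patient SD 10, visit SD 6-10, SD of a daily home mean 6 mmHg, source-population mean 140-150, independent daily errors, no clinic-home difference, and a systolic enrolment value from one occasion that is also the run-in reference.

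**Average overstatement.** With usual pressure U and enrolment value V, E[V − U | 140 ≤ V ≤ 170] = SDv² / (SDb² + SDv²) × (E[V | window] − μ).

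- μ = 140, SDv = 10: SD of V = 14.14. E[V | window] − μ = 14.14 × (0.3989 − 0.0420) / 0.4830 = 10.45. Half of this is 5.2 mmHg.
- μ = 150, SDv = 6: SD of V = 11.66. E[V | window] − μ = 11.66 × (0.2762 − 0.0917) / 0.7612 = 2.83. Times 36/136, this is 0.7 mmHg.
- μ = 155, the middle of the window: zero.

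**Simulation.** Patients are kept if V lies in 140-170. Run-in is passed if, within 15 days, five consecutive days average at least 10 below the reference, or alternatively if each of five consecutive days does. Relapse is three consecutive daily means at or above the reference within 15 days, after usual pressure is fully restored. The two enrolment-value columns are the ends of the range.

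| | Enrolment value: mean 150, visit SD 6 | Enrolment value: mean 140, visit SD 10 | 5-day home reference |
|---|---|---|---|
| No drug effect, passes run-in: 5-day mean | 15% | 42% | about 2% |
| No drug effect, passes run-in: each day | 3% | 20% | about 0.1% |
| True 10 mmHg effect, passes run-in: each day | 39% | 63% | 26% |
| Effect fully lost, scored as relapse: randomised by 5-day mean | 39% | 20% | 57% |
| Effect fully lost, scored as relapse: randomised by each day | 17% | 7% | 37% |

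Among all enrolled patients, before the run-in rule selects, a full return to usual pressure is scored 32-53% of the time, against 63% with the home reference. The further fall to 20-39% is the run-in rule's own selection.

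**What this does to events and power.** Take 80% and 40% as the true proportions losing a 10 mmHg effect, with 33 per arm: 33 × (0.80 + 0.40) = 39.6 true losses. Multiply by the proportion scored:

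- 5-day mean: 39.6 × 0.20 to 0.39 = 7.9 to 15.4 events, against 39.6 × 0.57 = 22.6
- Each day: 39.6 × 0.07 to 0.17 = 2.8 to 6.7, against 39.6 × 0.37 = 14.7

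The power formula above, applied to the scored rates (for example 0.80 × 0.20 = 16% against 0.40 × 0.20 = 8%: SEs 0.0800 and 0.0794, z = −0.97, power 17%), gives 17-32% against 50% for the 5-day mean, and 8-15% against 30% for each day. These are two-proportion illustrations, not the planned Cox analysis, and they leave out the further dilution from randomised non-responders.

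**Sensitivity.** Wider assumptions (source mean 130-150, between-patient SD 10-15, visit SD 6-12, daily SD 5-7, each-day rule, 7-day reference) give the same direction in every case: 6-14% scored as relapsed against about 42%.

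**The case against.** - **The run-in reference and the single reading are inferred.** This stands. Only relapse is tied to enrolment, and the text does not say how many readings form the value. Had it averaged several days before study drug, most of the problem would go; the plan describes no such average.
- **Regression to the mean may be small.** This stands too. The cap at 170 limits it, and at a source mean of 155 it vanishes. Patients with no effect would still pass 12-21% of the time under the 5-day-mean reading, because of noise in the reference. It would be wrong to put the whole effect down to selection for high pressure.
- **A clinic-home difference would make matters worse.** A reader might infer one, but the documents do not establish it. The timeline paragraph mentions testing readings from the supplied monitors, so the enrolment value may come from the same device. The figures assume no difference.
- **The three-day rule misses relapses anyway.** Correct: even with the home reference only 57% or 37% are scored. Only the gap between the columns belongs to the reference.
- **The plan has other protection.** Blood pressure is also analysed by a mixed model that needs no relapse threshold, and the period may be extended if recurrence is gradual. Both soften the loss. Neither repairs the primary outcome, and randomised non-responders dilute the mixed model as well.

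**Conclusion.** The concern holds as a loss of events and power, with the relapse reference as its source. A reader might infer that the comparison is biased towards PR or towards DC-1. The documents do not support that: randomisation follows the run-in rule, so the error is expected equally in every arm.

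The direction was the same in every scenario examined. The size rests on variance components that the documents do not give, on the enrolment value coming from one occasion, and on its use for the run-in fall. The two readings of the 10-point rule give clearly different sizes, and the text does not choose between them. The change is worth making before enrolment, but the power figures are illustrations, not estimates for this trial.

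**What to change.** For both the relapse outcome and the randomisation criterion, define the reference as the mean daily systolic pressure (the day's four readings averaged) from about five days on the study's home monitor. Take these readings between the first visit, when the monitor is taught, and the first capsule, and do not use them for eligibility. State that relapse and the 10-point fall are judged on the same daily mean, and whether the fall applies to a 5-day mean or to each day.

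Cost: a few days of home readings before the first capsule, which could fit in the week allowed between screening and admission, and possibly a separate dispensing contact because capsules are supplied at clinic visits. No new device is needed. Under the each-day reading fewer true responders pass run-in (about 26% against 39-63% for a 10 mmHg effect), so more patients must be screened. Under the 5-day-mean reading that pass rate changes little.

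The length-of-study text also lets relapse shorten a patient's experimental phase. The sponsor must reconcile any such use with the revised outcome definition; no clinical threshold is proposed here.
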